6.3.2.2. Definition of an SAE

An SAE is any untoward medical occurrence that, at any dose:

- a. Results in death (maternal, fetal, or neonatal in this study)
- b. Is life threatening

NOTE: The term “life threatening” in the definition of “serious” refers to an event in which the subject was at risk of death at the time of the event. It does not refer to an event, which hypothetically might have caused death, if it were more severe.

- c. Requires hospitalization or prolongation of existing hospitalization
- d. NOTE: In general, hospitalization signifies that the subject has been detained (usually involving at least an overnight stay) at the hospital or emergency ward for observation and/or treatment that would not have been appropriate in the physician’s

office or outpatient setting. Complications that occur during hospitalization are AEs. If a complication prolongs hospitalization or fulfills any other serious criteria, the event is serious. When in doubt as to whether “hospitalization” occurred or was necessary, the AE should be considered serious.

Hospitalization for elective treatment of a pre-existing condition that did not worsen from baseline is not considered an AE.

e. Results in disability/incapacity, or

NOTE: The term disability means a substantial disruption of a person’s ability to conduct normal life functions. This definition is not intended to include experiences of relatively minor medical significance such as uncomplicated headache, nausea, vomiting, diarrhea, influenza, and accidental trauma (e.g., sprained ankle) which may interfere or prevent everyday life functions but do not constitute a substantial disruption.

f. Is a congenital anomaly/birth defect

g. Medical or scientific judgment should be exercised in deciding whether reporting is appropriate in other situations, such as important medical events that may not be immediately life-threatening or result in death or hospitalization but may jeopardize the subject or may require medical or surgical intervention to prevent one of the other outcomes listed in the above definition. These should also be considered serious. Examples of such events are invasive or malignant cancers, intensive treatment in an emergency room or at home for allergic bronchospasm, blood dyscrasias or convulsions that do not result in hospitalization, or development of drug dependency or drug abuse.

h. All events of possible drug-induced liver injury with hyperbilirubinemia defined as ALT $\geq 3 \times$ ULN and bilirubin $\geq 2 \times$ ULN ($>35\%$ direct) (or ALT $\geq 3 \times$ ULN and international normalized ratio (INR) >1.5 , if INR measured) termed “Hy’s Law” events (INR measurement is not required and the threshold value stated will not apply to subjects receiving anticoagulants).

NOTE: The central laboratory report will include results for ALT, AST, ALP, total bilirubin, and direct bilirubin.

6.3.2.3. AEs of Special Interest

Certain AEs are of special interest for evaluating and characterizing the outcomes of women, fetuses, and/or neonates participating in this study. These AEs will be recorded on the events of special interest eCRFs pages in addition to the AE/SAE eCRF to capture additional details for the safety analyses.

Maternal, fetal, and neonatal AEs of special interest are listed in Section 6.3. Guidelines for reporting these events are provided in [Appendix 4](#).

6.3.3. Laboratory and Other Safety Assessment Abnormalities Reported as AEs and SAEs

Any abnormal laboratory test results (hematology, clinical chemistry, or urinalysis) or other safety assessments (e.g., ECGs, radiological scans, vital signs measurements),

including those that worsen from baseline values, and felt to be clinically significant in the medical and scientific judgment of the investigator are to be recorded as AEs or SAEs. However, any clinically significant safety assessments that are associated with the underlying disease, unless judged by the investigator to be more severe than expected for the subject's condition, are **not** to be reported as AEs or SAEs.

6.3.4. Cardiovascular Events

Investigators will be required to fill out event specific data collection tools for the following AEs and SAEs:

- Myocardial infarction/unstable angina
- Congestive heart failure
- Arrhythmias
- Valvulopathy
- Pulmonary hypertension
- Cerebrovascular events/stroke and transient ischemic attack
- Peripheral arterial thromboembolism
- Deep venous thrombosis/pulmonary embolism
- Revascularisation

Cardiovascular medical history/risk factors (as detailed in the eCRF) will be assessed at Screening. The cardiovascular eCRFs are presented as queries in response to reporting of certain cardiovascular Medical Dictionary for Regulatory Activities (MedDRA) terms. The cardiovascular information should be recorded in the specific cardiovascular section of the eCRF within 1 week of receipt of a cardiovascular event data query prompting its completion.

6.3.5. Death Events

In addition, all deaths (maternal, fetal, and neonatal) will require a specific death data collection tool to be completed. The death data collection tool includes questions regarding cardiovascular (including sudden cardiac death) and noncardiovascular death.

The death eCRF is provided immediately after the occurrence or outcome of death is reported. Initial and follow-up reports regarding death must be completed within 1 week of when the death is reported.

6.3.6. Congenital Anomalies

The proportion of infants with congenital anomalies diagnosed between the date of birth and 28 days post EDD will be assessed. Note: A congenital anomaly is a condition present at birth that results from malformation, deformation, or disruption in 1 or more parts of the body; a chromosomal abnormality; or a known clinical syndrome. Major congenital anomalies have a serious adverse effect on health, development, and

functional ability or may require surgical or medical management. Minor anomalies are physical findings that vary from norms in the general population but do not cause increased morbidity.

When a congenital anomaly is reported, it will be reviewed by an expert in teratology who serves as the birth defect evaluator for this study. The birth defect evaluator's responsibilities will include the review, evaluation, and classification of all reports of birth defects. Additionally, he/she will provide an opinion regarding the possible etiologies for the development of the observed anomalies. The birth defect evaluator will reference medically confirmed reports in making the evaluation and issue targeted queries to the infant's health care provider when necessary. If medical data are deemed insufficient to complete the evaluation, the birth defect evaluator may request additional medical evaluation of the infant.

For the purpose of this study, the US Centers for Disease Control and Prevention (CDC) Metropolitan Atlanta Congenital Defects Program (MACDP) criteria and the European Surveillance of Congenital Anomalies (EUROCAT) criteria will be used by the birth defect evaluator to code and classify congenital anomalies [[EUROCAT](#), 2005; [CDC](#), 2007].

Infants enrolled in the separate long-term infant follow-up study will be assessed for congenital anomalies diagnosed after 28 days post EDD.

6.3.7. Disease-Related Events and/or Disease-Related Outcomes Not Qualifying as SAEs

The DREs listed in Section [6.3.7.1](#) and Section [6.3.7.2](#) will be monitored by an internal GSK safety review team (reviewing blinded data).

6.3.7.1. Disease-Related Maternal Events

The following DREs are common maternal events during pregnancy, labor, and delivery:

- Signs and symptoms of labor discomfort (e.g., cramping, backache, muscle aches, nausea)
- Subsequent episodes of preterm labor (even if hospitalization is required) unless 1 of the conditions listed at the end of Section [6.3.7.2](#) applies
- Hospitalization for delivery, unless prolonged or 1 of the conditions listed at the end of Section [6.3.7.2](#) applies

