The active control in the study, atosiban, is a mixed oxytocin and vasopressin antagonist that is an EMA-approved drug marketed in the European Union since 2000. Atosiban is indicated to delay imminent preterm birth in pregnant adult women. No benefit to the neonate has been demonstrated in clinical trials using atosiban [Tractocile SmPC, 2013]. Subjects randomly assigned to this treatment group, therefore, will have the opportunity for a treatment benefit that will prolong pregnancy sufficiently to allow for antenatal corticosteroid treatment. The label indicates adverse reactions are generally mild, with nausea as the most commonly reported adverse maternal effect. Moreover, clinical trials did not reveal any specific adverse neonatal effects and long-term effects in the infant were in the range of normal variation and comparable with both placebo and β -agonists' rates.

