6.3.7.2. Disease-Related Neonatal Events (Occurring in Infants Born Prior to 37 Completed Weeks)

The following DREs are common neonatal events related to prematurity and can be serious or life threatening:

- Lungs and respiratory system
 - Apnea (severe)
 - Respiratory failure due to fatigue, hypoxia, or air leak from alveolar injury
- Cardiovascular
 - Patent ductus arteriosus
 - Bradycardia
- Neurological
 - Ventriculomegaly
 - Cerebellar hemorrhage
 - Hydrocephalus other than congenital
- Gastrointestinal
 - Gastroesophageal reflux
 - Aspiration pneumonia
- Hematologic
 - Anemia
- Vision
 - Retinopathy of prematurity (all stages)
- Auditory
 - Hearing disorder
- Other
 - Temperature instability
 - Hypoglycemia

Because these events (Section 6.3.7.1 and Section 6.3.7.2) are typically associated with preterm labor and prematurity, they will not be reported according to the standard process for expedited reporting of SAEs to GSK/PPD (even though the event may meet the definition of an SAE). These events will be recorded on the DRE page in the eCRFs. These DREs will be monitored by the internal GSK safety review team. ***However, if one or all of the following conditions apply, then the event should be reported as an AE/SAE using the standard process, as summarized in Section 6.3.11:***

- The event is, in the investigator's opinion, of greater intensity, frequency, or duration than expected for the individual subject,
- The investigator considers that there is a reasonable possibility that the event was related to treatment with the IP, or
- An event defined as a disease-related neonatal event is reported in an infant born ≥ 37 completed weeks.

If any of the above conditions are met, then record the event on the SAE page rather than the DRE page and report promptly (i.e., expedited reporting, see Section [6.3.11](#)) to GSK/PPD.

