8.2.3.7. Disease-Related Events and/or Disease-Related Outcomes Not Qualifying as SAEs

Maternal and neonatal disease-related events (DREs) described below will be reported in a similar manner as all AEs. A listing of DREs will be provided. Also, the above summary will be produced by subgroups defined in Section **Error! Reference source not found.**

The DREs will be summarized by maternal and neonatal events, separately.

The following DREs are common maternal events during pregnancy, labor, and delivery:

- Signs and symptoms of labor discomfort (e.g., cramping, backache, muscle aches, nausea)

- Subsequent episodes of preterm labor (even if hospitalization is required) unless 1 of the conditions listed at the end of Protocol Section 6.3.7.2 applies
- Hospitalization for delivery, unless prolonged or 1 of the conditions listed at the end of Protocol Section 6.3.7.2 applies Signs and symptoms of labor discomfort (e.g., cramping, backache, muscle aches, nausea)

The following DREs are common neonatal events related to prematurity and can be serious or life threatening:

- Lungs and respiratory system
 - Apnea (severe)
 - Respiratory failure due to fatigue, hypoxia, or air leak from alveolar injury
- Cardiovascular
 - Patent ductus arteriosus
 - Bradycardia
- Neurological
 - Ventriculomegaly
 - Cerebellar hemorrhage
 - Hydrocephalus other than congenital
- Gastrointestinal
 - Gastroesophageal reflux
 - Aspiration pneumonia
- Hematologic
 - Anemia (severe)
- Vision
 - Retinopathy of prematurity (all stages)
- Auditory
 - Hearing disorder
- Other

- Temperature instability
- Hypoglycemia

These events will be recorded on the DRE page in the maternal or neonatal eCRFs. These DREs will be monitored by the IDMC and internal safety review committee. However, if one or all of the following conditions apply, then the event should be reported as an AE/SAE using the standard process:

- The event is, in the investigator's opinion, of greater intensity, frequency, or duration than expected for the individual subject,
- The investigator considers that there is a reasonable possibility that the event was related to treatment with the IP, or
- An event defined as a disease-related neonatal event is reported in an infant born ≥ 37 completed weeks.

If any of the above conditions are met, then record the event on the SAE page rather than the DRE page and report promptly.

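### Investigator attribution can split maternal nausea between the AE and DRE tables with no pooled by-arm count planned, and the DRE exception rule sends nonserious events to the SAE page

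*Protocol*

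**What the plan says.** Protocol 1.3.2 says of atosiban: "The label indicates adverse reactions are generally mild, with nausea as the most commonly reported adverse maternal effect". Protocol 6.3.7.1 lists among the maternal DREs "Signs and symptoms of labor discomfort (e.g., cramping, backache, muscle aches, nausea".

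Protocol 6.3.7.2 applies one recording rule to the maternal and neonatal lists together: "These events will be recorded on the DRE page in the eCRFs". Two exceptions can apply to a mother. Either the event is "of greater intensity, frequency, or duration than expected for the individual subject", or "The investigator considers that there is a reasonable possibility that the event was related to treatment with the IP". The third exception concerns infants born at 37 completed weeks or later. An excepted event is first directed to ordinary AE or SAE reporting under 6.3.11. The section then closes with a different instruction: "If any of the above conditions are met, then record the event on the SAE page rather than the DRE page and report promptly". SAP 8.2.3.7 repeats that closing instruction.

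On analysis, Protocol 8.3.5.2.2 summarizes DREs in the same way as AEs. SAP 8.2.3.7 also reports them like AEs, and adds: "The DREs will be summarized by maternal and neonatal events, separately". SAP Appendix 11 plans Tables 3.11 (maternal AEs), 3.41 (most common maternal AEs), 3.51 (maternal SAEs) and 3.81 (maternal DREs), all on the Maternal Safety population, with Listings 41 (maternal AEs) and 57 (maternal DREs).

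**The concern.** The same symptom is both a known reaction to the comparator and an expected feature of the condition under study. In a woman in preterm labor on a blinded infusion, attribution decides which eCRF page receives it. A reader of Tables 3.11 and 3.41 would naturally take the nausea row as the incidence of nausea. If DRE-page records are left out, that row is only the part that investigators judged possibly drug-related or out of the ordinary.

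Describing maternal safety against atosiban is a secondary objective (Protocol 2.2), and nausea is the one maternal reaction that the protocol singles out for the comparator.

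The closing sentence of 6.3.7.2 raises a second problem, which affects every DRE term and not only nausea. Taken literally, mild nausea thought to be related to treatment would be entered as an SAE.

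**Working it through.** There is no plan figure to reproduce: neither document gives a nausea rate or the share of events expected on each page. The check traces nausea from definition to display.

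**1. Which page.** Protocol 6.3.2.1 keeps expected symptoms of the studied disorder out of AEs unless they are more severe than expected. Sections 6.3.7.1 and 6.3.7.2 put labor-discomfort nausea on the DRE page unless one of the two maternal exceptions applies. Both exceptions are investigator judgements, so the split is by attribution.

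**2. Which table.** SAP 8.2.3.1 reports AEs by system organ class, preferred term and arm, and SAP 8.2.3.7 treats DREs likewise. Both parts of the split are therefore shown by arm, in different tables. No section says whether Table 3.11 draws on DRE-page records.

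**3. Effect on the AE tables if DRE-page records are excluded.** Let p_A and p_R be the true proportions of women with nausea on atosiban and retosiban, and f_A and f_R the fractions of those women whose nausea reaches the AE page.

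- The AE table shows f_A·p_A and f_R·p_R, each no greater than the true value.
- If f_A = f_R = f, the displayed difference is f·(p_A − p_R) and the displayed ratio is still p_A/p_R.
- If the fractions differ, both difference and ratio can move, and the direction is not determined.

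**4. Why the tables cannot be added.** SAP 8.2.3 counts a woman once at each level of a table. For women with nausea on either page, n_either = n_AE + n_DRE − n_both. No planned table gives n_both, so the tables only bound the answer: max(n_AE, n_DRE) ≤ n_either ≤ n_AE + n_DRE. One event should not sit on both pages, but a woman with two separate episodes can appear in both tables.

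**5. The display threshold in Table 3.41.** SAP 8.2.3.3 shows on-treatment AEs above 2%. With 97 women randomized 1:1, an arm has about 97/2 ≈ 48. Read per arm, 1/48 = 2.1%, so a single AE-page case keeps nausea in the table. Read over both arms, 1/97 = 1.0% and 2/97 = 2.1%, so two cases are needed.

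**6. The SAE-page sentence against its neighbors.**

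| Place | Route for a nonserious event thought related to treatment |
|---|---|
| Protocol 6.3.7.2, exception sentence | Ordinary AE or SAE reporting under 6.3.11 |
| Protocol 6.3.11, Table 6 | Adverse Reaction tool, 5 calendar days (SAEs: 24 hours) |
| Protocol 6.3.2.2 | Not an SAE unless a seriousness criterion is met |
| Protocol 6.3.7.2, last sentence; SAP 8.2.3.7 | SAE page, prompt reporting, no seriousness condition |

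The last row is incompatible with the other three. If sites followed it, Table 3.51 could hold nonserious events.

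**The case against.** A reader might infer that nausea is omitted from the safety output, or that no table gives its incidence by arm. The documents do not support that. Table 3.81 stands under the maternal AE heading, is reported in the manner of AEs, and remains in the display list kept after termination. Listing 57 gives the individual records. What is missing is one combined figure, and it could be rebuilt by hand from Listings 41 and 57.

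A reader might also take it as settled that Table 3.11 excludes DRE-page records. That is an inference from the separate displays. SAP Table 5 lists disease-related AEs under its AE heading, so the other reading is possible.

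The DRE item covers nausea as a symptom of labor discomfort, not nausea of any cause, and suspected drug-related nausea has a stated route to AE reporting. The trial is double-blind, so attribution is made without knowledge of arm, which makes similar fractions in the two arms plausible. The objective is descriptive and no formal safety tests are planned (Protocol 8.3.5.2, SAP 5.2). All of this stands and limits the stakes.

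On the SAE page, it can be said that Table 6 already gives the correct route. It does, but the last sentence of 6.3.7.2 and its copy in the SAP still say otherwise.

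**Conclusion.** The point holds as a split, not an omission. Attribution decides whether maternal nausea is recorded as a DRE or as an AE, the SAP is silent on whether Table 3.11 covers both pages, and no pooled by-arm incidence is planned. If Table 3.11 excludes DRE-page records, the AE tables understate nausea in any arm where some cases stay on the DRE page, and they shrink the absolute difference if the fraction reaching the AE page is the same in both arms. If Table 3.11 includes them, the remaining defect is that the SAP does not say so.

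No numerical size can be given. Any attenuation figure would need assumed nausea rates and an assumed capture fraction, and the documents supply neither. Loss of nausea from Table 3.41 is a narrow risk. Read per arm, it requires that no woman has AE-page nausea on treatment; read over both arms, at most one.

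The SAE-page instruction is a plain contradiction within the protocol, carried into the SAP, and is wrong as written.

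It is tempting to conclude that nausea should come off the DRE list. That would not help here. The trial was terminated, so rewording the list cannot change how recorded events were classified, and 6.3.2.1 would still keep expected symptoms of labor out of AEs.

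**What to change.** 1. In SAP 8.2.3.1 and 8.2.3.7, state whether Table 3.11 includes DRE-page records. Add a supplementary by-arm summary that pools AE, SAE and DRE pages by preferred term for nausea and the other maternal DRE terms. Count each woman once per term, and use the on-treatment window already defined in SAP 11.3.3.
2. Reconcile the last sentence of Protocol 6.3.7.2 and its copy in SAP 8.2.3.7 with Protocol 6.3.2.2 and Table 6. State in SAP 8.2.3.4 that Table 3.51 counts only events meeting a seriousness criterion.

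The cost is one small table and a few sentences. The SAP places analysis decisions before database freeze, so the SAP changes can be made up to that point. The pooled summary assumes that DRE-page entries carry a term that can be coded to nausea, which should be confirmed. Its downside is that it also counts nausea from labor itself, which may not be equal between arms if the drugs differ in suppressing labor. It should therefore be shown beside Tables 3.11 and 3.81, not in place of them.

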6.3.7.2. Disease-Related Neonatal Events (Occurring in Infants Born Prior to 37 Completed Weeks)

The following DREs are common neonatal events related to prematurity and can be serious or life threatening:

- Lungs and respiratory system
 - Apnea (severe)
 - Respiratory failure due to fatigue, hypoxia, or air leak from alveolar injury
- Cardiovascular
 - Patent ductus arteriosus
 - Bradycardia
- Neurological
 - Ventriculomegaly
 - Cerebellar hemorrhage
 - Hydrocephalus other than congenital
- Gastrointestinal
 - Gastroesophageal reflux
 - Aspiration pneumonia
- Hematologic
 - Anemia
- Vision
 - Retinopathy of prematurity (all stages)
- Auditory
 - Hearing disorder
- Other
 - Temperature instability
 - Hypoglycemia

Because these events (Section 6.3.7.1 and Section 6.3.7.2) are typically associated with preterm labor and prematurity, they will not be reported according to the standard process for expedited reporting of SAEs to GSK/PPD (even though the event may meet the definition of an SAE). These events will be recorded on the DRE page in the eCRFs. These DREs will be monitored by the internal GSK safety review team. ***However, if one or all of the following conditions apply, then the event should be reported as an AE/SAE using the standard process, as summarized in Section 6.3.11:***

- The event is, in the investigator's opinion, of greater intensity, frequency, or duration than expected for the individual subject,
- The investigator considers that there is a reasonable possibility that the event was related to treatment with the IP, or
- An event defined as a disease-related neonatal event is reported in an infant born ≥ 37 completed weeks.

If any of the above conditions are met, then record the event on the SAE page rather than the DRE page and report promptly (i.e., expedited reporting, see Section [6.3.11](#)) to GSK/PPD.

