11.11.5. Safety Tables

Safety Tables					
No.	Population	IDSL / TST ID / Example Shell	Title	Programming Notes	Deliverable [Priority]
Exposure					
3.01	Maternal Safety		Summary of Extent of Study Drug Exposure		
3.02	Maternal Safety		Summary of Inadequate Therapeutic Response		
Maternal Adverse Events					
3.11	Maternal Safety		Summary of Maternal Adverse Events		
3.31	Maternal Safety		Summary of Maternal Adverse Events by Maximum Grade or Intensity		
3.41	Maternal Safety		Summary of Most Common Maternal Adverse Events		
3.51	Maternal Safety		Summary of Maternal Serious Adverse Events		
3.71	Maternal Safety		Summary of Maternal Adverse Events of Special Interest		
3.72	Maternal Safety		Summary of Maternal Adverse Events of Special Interest by Gestational Age Group		

CONFIDENTIAL

GSK200721

Safety Tables					
No.	Population	IDSL / TST ID / Example Shell	Title	Programming Notes	Deliverable [Priority]
3.81	Maternal Safety		Summary of Maternal Disease-Related Adverse Events		
Fetal Adverse Events					
3.111	Maternal Safety		Summary of Fetal Adverse Events		
3.131	Maternal Safety		Summary of Fetal Adverse by Maximum Grade or Intensity		
3.141	Maternal Safety		Summary of Most Common Fetal Adverse Events		
3.151	Maternal Safety		Summary of Fetal Serious Adverse Events		
3.171	Maternal Safety		Summary of Fetal Adverse Events of Special Interest		
3.172	Maternal Safety		Summary of Fetal Adverse Events of Special Interest by Gestational Age Group		
Neonatal Adverse Events					
3.211	Neonatal Safety		Summary of Neonatal Adverse Events		
3.231	Neonatal Safety		Summary of Neonatal Adverse by Maximum Grade or Intensity		

CONFIDENTIAL

GSK200721

Safety Tables					
No.	Population	IDSL / TST ID / Example Shell	Title	Programming Notes	Deliverable [Priority]
3.241	Neonatal Safety		Summary of Most Common Neonatal Adverse Events		
3.251	Neonatal Safety		Summary of Neonatal Serious Adverse Events		
3.271	Neonatal Safety		Summary of Neonatal Adverse Events of Special Interest		
3.272	Neonatal Safety		Summary of Neonatal Adverse Events of Special Interest by Gestational Age Group		
3.281	Neonatal Safety		Summary of Neonatal Disease-Related Adverse Events		
Maternal Hospital Admission					
3.301	Maternal Safety		Summary of Maternal Hospital Admission (In-patient)		
Labs					
3.401	Maternal Safety		Summary of Observed Value and Change from Baseline in Hematology by Visit		
3.402	Maternal Safety		Summary of Hematology Results Outside the Reference Ranges by Visit		

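### For the listed disease-related neonatal events, the 37-week booking rule shifts the AE and SAE tables against the arm with more term births, and no planned table pools them

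*Protocol*

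**What the plan says.** Protocol 6.3.7.2 lists neonatal events regarded as common in prematurity. They include severe apnea, respiratory failure, patent ductus arteriosus, bradycardia, ventriculomegaly, cerebellar hemorrhage, reflux, anemia, retinopathy and hypoglycemia. For infants born before 37 completed weeks, "These events will be recorded on the DRE page in the eCRFs", outside expedited SAE reporting even when the event would meet the SAE definition.

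Three conditions move an event to AE/SAE reporting:
- it is "of greater intensity, frequency, or duration than expected for the individual subject";
- the investigator thinks it may be related to the investigational product;
- "An event defined as a disease-related neonatal event is reported in an infant born" at or after 37 completed weeks.

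The text first says such an event is reported as an AE/SAE. It then says "then record the event on the SAE page rather than the DRE page and report promptly". SAP 8.2.3.7 repeats the conditions and the change of page.

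On tabulation, SAP 8.2.3.7 says "The DREs will be summarized by maternal and neonatal events, separately". SAP 11.11.5 lists table 3.211 (all neonatal AEs), table 3.251 ("Summary of Neonatal Serious Adverse Events") and table 3.281 (neonatal DREs). None pools AEs with DREs, and SAP 11.11 limits output to the displays it lists. The one safety subgroup named in SAP 5.1.2 is gestational age at randomization. Gestational age at delivery, an optional safety subgroup in Protocol 8.3.5.2, is not named there, although SAP 5.1.2 leaves room for further subgroups.

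**The concern.** The primary objective is to prolong pregnancy, and birth before 37 weeks is a key secondary endpoint. The variable that decides the page is therefore a post-randomization outcome that treatment is expected to affect. If one arm has more term births, more of its listed events go to the AE and SAE tables and fewer to the DRE table, even if the risk at a given gestation is the same in both arms.

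Neonatal safety is a secondary objective and is described without formal tests, so these tables are the planned comparison. For the same preferred term they can point in different directions, and no listed display gives the total by arm.

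There is also a wording conflict that needs no arithmetic. Read literally, the instruction to use the SAE page would put a non-serious listed event in a term infant, such as mild reflux, among the serious events.

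**Working it through.** The documents state no figure to reproduce, so this is an expected-rate calculation for the listed terms only.

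**Inputs**
- Preterm share P: 60% atosiban, 45% retosiban. These are assumptions; the plan gives no preterm share for this comparison.
- Risk of a listed event: rp = 30% if preterm, rt = 6% if term, the same in both arms. These are assumptions.
- Share q of preterm events escalated to AE/SAE reporting (worse than expected, or possibly product-related). It is not given, so it is varied from 0 to 25%.
- Enrolment: 97 women randomized 1:1 (SAP 1 and 2.3), about 48 per arm.

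**Formulas**
- Pooled rate = P·rp + (1−P)·rt
- AE/SAE-page rate = P·q·rp + (1−P)·rt
- DRE-page rate = P·(1−q)·rp
- Shift in the between-arm difference on the AE/SAE page, relative to pooling = (difference in P)·(1−q)·rp

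**Results (atosiban vs retosiban; RR is retosiban/atosiban)**

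| Display | Atosiban | Retosiban | RR |
|---|---|---|---|
| Pooled | 0.60×0.30 + 0.40×0.06 = 20.4% | 0.45×0.30 + 0.55×0.06 = 16.8% | 0.82 |
| AE/SAE page, q = 0 | 0.40×0.06 = 2.4% | 0.55×0.06 = 3.3% | 1.38 |
| AE/SAE page, q = 25% | 4.5% + 2.4% = 6.9% | 3.4% + 3.3% = 6.7% | 0.97 |
| DRE page, q = 0 | 0.60×0.30 = 18.0% | 0.45×0.30 = 13.5% | 0.75 |

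The shift against retosiban is 0.15×0.30 = 4.5 percentage points at q = 0 and 0.15×0.75×0.30 = 3.4 points at q = 25%.

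**When the sign reverses.** The AE/SAE-page rate can be written rt + P·(q·rp − rt). It does not depend on P when q = rt/rp = 0.06/0.30 = 20%. Below that the page points the wrong way. Above it the direction is right but the benefit is understated.

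**Size in this trial.** With 48 per arm and q = 0, the page shows 48×0.024 = 1.2 against 48×0.033 = 1.6 infants, a gap of about 0.4 infant.

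**Sensitivity.** Protocol 1.2 gives Phase II preterm shares of 47.2% (placebo) and 18.7% (retosiban). With those shares and q = 0, the page ratio is 81.3/52.8 = 1.54, the DRE ratio is 18.7/47.2 = 0.40 and the pooled ratio is 10.5%/17.3% = 0.61. Keeping those shares and varying rp over 20–60% and rt over 2–10%, the pooled ratio runs from 0.44 to 0.81. The shift runs from 5.7 to 17.1 points at q = 0 and from 4.3 to 12.8 points at q = 25%. With equal preterm shares there is no shift.

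**The case against.** **A reader might infer that retosiban's overall neonatal AE and SAE rates would rise through booking alone.** The documents do not support that. Under Protocol 6.3.2.3, events of special interest (including RDS, IVH, bronchopulmonary dysplasia, necrotizing enterocolitis and infections) go on the AE/SAE form with no condition on gestation at birth, and they fill the same tables. As an illustration, add one independent class of such events with the same 30% and 6% risks, at q = 0. The chance of any AE/SAE is then 30% in a preterm infant and 1 − 0.94² = 11.64% in a term infant. The arm rates are 0.60×0.30 + 0.40×0.1164 = 22.7% and 0.45×0.30 + 0.55×0.1164 = 19.9%, RR 0.88. Full pooling gives RR 0.83. That is attenuation, not reversal.

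**Escalation weakens the effect.** Some preterm events do reach the AE/SAE tables, and the reversal disappears once 20% or more are escalated in the main example. The true share is unknown.

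**The data are not lost.** DREs are shown by arm in table 3.281 and listing 96. Adding the 3.211 and 3.281 rows for a preferred term nearly gives the pooled count. It double-counts only an infant with the same term on both pages. Qualifying cerebellar hemorrhage, retinopathy and persistent ventriculomegaly also enter the neonatal composite (table 2.101), which is taken from medical records whatever the gestation at birth. What cannot be recovered by adding rows is the organ-class total or the any-event total.

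**The trial is small and its safety analysis is descriptive.** This limits the practical weight of the point but does not remove the shift.

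It would also be wrong to call the lower DRE rate purely an artefact. In the example the true ratio is already 0.82, and the split takes it to 0.75.

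**Conclusion.** The point holds for the listed DRE terms. Their booking depends on a treatment outcome, so tables 3.211 and 3.251 are shifted against the arm with more term births and table 3.281 overstates that arm's advantage. The direction follows from the rule whenever preterm shares differ, risk at a given gestation is alike in the two arms, and not every preterm event is escalated. The size rests on assumed shares and risks; the Phase II shares come from a placebo comparison, not from atosiban. The calculation does not separate serious from non-serious events. How far table 3.251 is affected depends on that mix and on which reading of the page instruction sites followed.

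At the enrolled size the main example moves less than half an infant on the AE/SAE page. This is a worthwhile, inexpensive improvement, not a flaw that invalidates the safety analysis. The conflict between AE/SAE reporting and the SAE page is a separate, certain inconsistency in both documents.

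**What to change.** - In SAP 8.2.3 and Appendix 11, add one neonatal table pooling AEs and DREs by system organ class, preferred term and arm. Count each infant once per term, regardless of gestational age at birth or CRF page.
- Footnote tables 3.211, 3.251 and 3.281 to say that booking of listed events depends on gestational age at birth.
- Add a pooled serious-event table only if the DRE page captures seriousness, which the documents do not show. Do not pool SAEs with all DREs. Non-serious events would then count in preterm infants but, if booked as ordinary AEs, not in term infants, which is the opposite bias.
- Reconcile the sentences in Protocol 6.3.7.2 and SAP 8.2.3.7 that refer first to AE/SAE reporting and then to the SAE page. For data already collected, state in the report how non-serious listed events in term infants were recorded.

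The cost is one table from data already collected, three footnotes and some wording. The drawback is a longer table that includes expected events of prematurity. SAP 9 rules out changes to the planned analyses after the blind is broken, so the table should be added before then.
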